9.6 Data Analyses

Primary Analyses

Our primary analyses will use mixed-effects regression models (MRMs) with a logistic linking function (a GLMM analysis) since our primary outcome measure (response to treatment, defined as CGI-I≤2) is dichotomous. Analyses of secondary outcomes will be performed using MRM. MRM and GLMM easily accommodate nesting of repeated observations within subjects, include all subjects with at least one assessment, and are the preferred method to analyze longitudinal data (Hamer and Simpson, 2009 [135]). Since these analyses will include all subjects who are randomized and complete at least one assessment, it is an intent-to-treat analysis. Also, since subjects will undergo treatment in groups (4-6 subjects per group) our MRM and GLMM models will include 3 levels: repeated measurements (level 1) nested within subjects (level 2) who will be nested within their treatment cohort (level 3).

Our primary model will be a GLMM in which response to treatment over time will be modeled as a growth curve. Our primary analyses will examine outcomes at post-treatment (Aim 1). These analyses will include only the 7 assessments from baseline to post-treatment, and will not include the follow-up (FU) assessment since it could be affected by subjects seeking other treatments during the FU period. Only our exploratory analyses for outcome at FU (Aim 2) will include data from the FU assessment. Since recent research indicates that suboptimal modeling of the growth curve can result in incorrect results, we will examine various linear and nonlinear models to find the optimal growth curve during treatment (linear, quadratic, cubic, exponential [leveling off at an asymptote], and an ANOVA model, in which time is coded as a categorical variable. For this ANOVA model, each assessment time point is modeled with a dummy coded assessment variable [coded 1 for the assessment, 0 for other assessments]. In this model, the means at each assessment point are freely estimated and are not constrained to fit any particular pattern. See our discussion of the ANOVA model in the paragraph below for more information).We will conduct our significance tests using the growth curve that most accurately models the data (comparing the various growth curve models using AIC and BIC).

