The three treatment conditions (Yoga, CBT, and SE) will be coded using 2 dummy variable contrasts, with SE as the "reference" treatment. The first dummy variable will contrast Yoga vs. SE, and the second will contrast CBT to SE. Time will be coded as weeks since baseline. To test of differences between treatments at post-treatment (week 12), time will be centered at week 12 (in other words, our Time variable in our analysis will be computed as "time minus 12"). In MRM or GLMM analyses in which this Time centered variable is used, the significance of the dummy variable contrasts (Yoga vs. SE and CBT vs. SE) provides the test of the differences between treatment conditions at post-treatment. A similar approach can be used to test differences between treatment conditions at follow-up.

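### Centering Time at week 12 is not guaranteed to make the arm dummies the week-12 contrast if the exponential growth curve is selected

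*Combined protocol and SAP*

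**What the plan says.** All of this is in section 9.6 (Data Analyses) of the combined protocol and SAP.

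- **Target.** "Our primary analyses will examine outcomes at post-treatment (Aim 1"), and "These analyses will include only the 7 assessments from baseline to post-treatment".
- **Candidate curves.** "linear, quadratic, cubic, exponential [leveling off at an asymptote], and an ANOVA model, in which time is coded as a categorical variable".
- **Choice of curve.** "We will conduct our significance tests using the growth curve that most accurately models the data (comparing the various growth curve models using AIC and" BIC).
- **Time coding.** "time will be centered at week 12 (in other words, our Time variable in our analysis will be computed as" weeks minus 12.
- **Term tested.** In any MRM or GLMM that uses the centered variable, "the significance of the dummy variable contrasts (Yoga vs. SE and CBT vs. SE) provides the test of the differences between treatment conditions" at post-treatment.

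The rule makes no exception for the exponential candidate, and no equation is given for that curve. Section 9.6 describes a different test, the arm-by-assessment interaction, for categorical time. It also plans a secondary logistic regression of post-treatment response that uses no growth curve.

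**The concern.** In a model with an arm dummy and an arm-by-curve interaction, the dummy is the arm difference at the point where the curve term is zero. Centering Time at week 12 puts that point at week 12 only if every time term vanishes at Time = 0. Polynomial terms do. An exponential that is "exponential [leveling off at an asymptote" may or may not, depending on how it is written.

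Hypotheses 1.1 and 1.2 are defined at post-treatment. If the exponential is selected and coded so that its term vanishes only at the asymptote, the rule as written would judge those hypotheses on an effect extrapolated beyond the end of treatment. Two analysts could both follow section 9.6 and test different hypotheses on the same data.

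**Working it through.** **Inputs.** From section 9.6: the candidate curves, selection by AIC/BIC, Time = t − 12 with t in weeks, the week-12 target, seven assessments and the logit link. Not stated, so assumed here: the equation of the exponential, its rate k, the starting level, and which parameters differ by arm.

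**Plan's own figures.** The plan gives no figure on this point. The sample size that can be rebuilt is the 95 per arm for non-inferiority in section 9.2: (1.645 + 0.842)² × 2 × 0.579 × 0.421 / 0.1785² = 94.6, rounded up to 95. This takes one-sided 0.05, which the plan does not state. Nothing below depends on it.

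**1. General form.** Let D be an arm dummy and log-odds = b0 + b1·D + b2·g(Time) + b3·D·g(Time). The arm difference at any time is b1 + b3·g(Time), so b1 is the difference where g = 0.

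**2. Polynomials.** Time, Time² and Time³ are all 0 at Time = 0. So b1 is the week-12 difference and the rule is correct.

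**3. Exponential entered as g = exp(-k·Time).** At week 12, g = 1, so the week-12 difference is b1 + b3. The term reaches 0 only as time goes to infinity, so b1 is the difference at the asymptote. Centering does not change this: exp(-k(t − 12)) = exp(12k)·exp(-kt), which only rescales the regressor and leaves b1 as it was.

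**4. Exponential parameterised by its value at Time = 0.** With g = 1 − exp(-k·Time), g = 0 at week 12. So b1 is the week-12 difference and the rule is correct.

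**5. Noise-free check.** Take k = 0.15, a common start of −3.5 at week 0, and asymptotes of 0.2 and 1.5 on the log-odds scale.
- Asymptote difference: 1.5 − 0.2 = 1.300.
- Week-12 difference: 1.3 × (1 − exp(−1.8)) = 1.3 × 0.8347 = 1.085.
- Fitting the seven visits gives a dummy of 1.300 under step 3 and 1.085 under step 4. The fitted curves are the same but the quantity tested differs.

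**6. Size with equal starts and a common rate.** Asymptote difference / week-12 difference = 1/(1 − exp(−12k)).
- Half-life 3 weeks: exp(−12k) = 0.5⁴ = 0.0625, ratio 1/0.9375 = 1.07.
- Half-life 6 weeks: exp(−12k) = 0.5² = 0.25, ratio 1/0.75 = 1.33.

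**7. Unequal rates.** Let both arms start at 2% (log-odds −3.892) and both reach 50% at week 12 (log-odds 0), with rates 0.3 and 0.1. The asymptote is −3.892 + 3.892/(1 − exp(−12k)).
- k = 0.3: −3.892 + 3.892/0.9727 = 0.109, or 53%.
- k = 0.1: −3.892 + 3.892/0.6988 = 1.677, or 84%.

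The arms do not differ at week 12 but differ by 1.57 in log-odds at the asymptote. This applies only if the fitted model lets the rate differ by arm.

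**8. Direction of the power effect.** Use a linear approximation with a known common rate and ratings at weeks 2, 4, …, 12. Per-arm variance multipliers for the asymptote and for week 12 are 0.473 and 0.346 (3-week half-life), and 1.277 and 0.423 (6-week). With compound-symmetric within-patient correlation ρ, the variance is (1 − ρ) × multiplier + ρ.
- ρ = 0: SE ratios √(0.473/0.346) = 1.17 and √(1.277/0.423) = 1.74. Both exceed the effect ratios 1.07 and 1.33, so the asymptote test is weaker.
- ρ = 0.5: SE ratios √(0.7365/0.673) = 1.046 and √(1.1385/0.7115) = 1.265. Both are below 1.067 and 1.333, so the asymptote test is no weaker.

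**The case against.** The plan's intent is explicit: section 9.6 names week 12 as the time of the comparison, and an asymptote test would contradict that. The problem needs two things to happen: the exponential must be selected, and it must be coded in the asymptote form. If the curve has flattened by week 12, the two contrasts nearly coincide. If starts and rate are common to the arms, the two differences are proportional, so the null hypothesis is the same. The planned logistic regression of post-treatment response, run with last observation carried forward and in completers, would show a discrepancy.

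Much of this stands, and it limits two stronger readings.

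- A reader might infer that under the exponential curve the dummy simply is the asymptote difference. The documents do not support that. They give no equation, and under the form in step 4 the rule works as written.
- A reader might infer a definite loss of power for the primary test. The documents do not support that either. The .80 power figures in section 9.2 concern the non-inferiority test and the continuous secondary outcomes, not superiority on response. Step 8 shows that the direction of the effect changes with within-patient correlation, and the planned model nests repeated measurements within subjects.

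What does not stand is that stated intent settles the matter. The rule names the model term to be tested, covers every analysis that uses centered Time, and is false for one natural way of putting the exponential into a GLMM linear predictor. The logistic regression is secondary, so it can expose a discrepancy but does not replace the primary test.

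**Conclusion.** The point holds in a limited form. The centering rule is correct for the polynomial candidates and is not guaranteed for the exponential one. In the exp(-k·Time) form the tested quantity is the asymptote difference. With equal starts and a common rate, that is about 1.07 times the week-12 difference at a 3-week half-life and 1.33 times at 6 weeks. The half-lives are illustrative, since the plan states no rate. If rates differ by arm, the two contrasts can disagree on whether there is any difference at all.

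The effect on power depends on the rate, the within-patient correlation and the effect size. It may be negligible, and no figure for it should be quoted. What needs correcting is that the primary superiority test is not tied to post-treatment under every curve the plan allows. The harm is conditional on curve selection and coding, but it touches the primary test and is nearly free to remove, so the plan should be changed.

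**What to change.** In section 9.6, where the arm contrasts are defined, state that for whichever growth curve is selected the primary superiority test is the model-estimated arm difference in log-odds of response at week 12. This is the arm term plus the arm-by-curve terms evaluated at week 12, with a delta-method standard error where an estimated rate enters the contrast. Equivalently, write out the exponential equation and code its time term to be zero at week 12, for example 1 − exp(-k·Time) with Time = weeks − 12, so that the existing rule becomes true.

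The cost is one sentence in the SAP and one contrast statement in the analysis code. It needs no new data and no change to the sample size.

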6. STUDY PROCEDURES

6.1. Schedule of Evaluations

Form Type	Measure	Admin By	Mo. -1 (Scree n*)	Wk 0 (Baseline)	Wks 1-5	Wk 6 (Mid Tx)	Wks 7-11	Wk 12-13 (Post Tx)	Wk 36-37 (6 mo. FU)
Diagnosis & Screening	Eligib ility/Informed Consent	IE + RA pre- screen	Х						
	SCID/ADIS-5	IE	Х						
	CGI-S/CGI-I ^{1,} 2	IE	Х	Х	X (biweekly)	Х	X (biweekly)	Х	Х
	SIGH-A	IE	Х	Х	(orweekiy)	Х		Х	Х
	Demographics	Self	Х						
	Medical History	MD/RN	Х						
	Screening Medications/T herapy Log	MD/RN	Х						
	Physical Exam	MD/RN	Х						
	MoCA	MD/RN	Х						
Secondary	STAI	Self		Х		Х		Х	Х
Outcomes	BAI	Self		Х	X X (biweekly)	X (biweekly)	Х	Х	
	BDI-II	Self	Х	Х	(;))	Х	())	Х	Х
	PSS	Self		Х		Х		Х	Х
	WHOQOL- BREF	Self		Х		Х	Х	Х	
	SCL-90	Self		Х		Х		Х	Х
	PSWQ	Self		Х	X (weekly if in CBT)	Х	X (weekly if in CBT	Х	Х
	ISI	Self		Х	,			Х	
	PSQI	Self		Х				Х	
	SOCI	Self						Х	
	ASQ	Self		Х		Х		Х	Х
Mediators	MCQ	Self		Х		Х		Х	Х
	FFMQ	Self		Х		Х		Х	Х
Psycho-	ECG (RSA)	RA		Х		Х		Х	Х
physiological & Biological	Salivette Sample	Self		Х		Х		Х	Х
stress	Affect Grid	RA		Х		Х		Х	Х
	Vital Signs	RA		Х		Х		Х	Х
Tx Details	Credibility / Expectancy	Self		Х		Х		Х	Х
	Homework compliance	Self			X (weekly)	Х	X (weekly)	Х	
Safety & Integrity	Adverse Events Log ³	RA		Х	X (weekly)	Х	X (weekly)	Х	Х

	Concomitant Medications/T herapy Log ³	RA		Х	X (weekly)	Х	X (weekly)	Х	Х
	Suicidality checklist ²	IE	Х	Х	X (biweekly)	Х	X (biweekly)	Х	Х
	Working alliance	Self			(0111001115)	Х	(011100111))	Х	
	SAFETY Form	RA		Х	X (weekly)	Х	X (weekly)	Х	Х
	End of Study	RA			Compl	eted afte	er 6-month FU/ear	ly termination	on visit
	Protocol Deviations	RA					Ad hoc, as needed	ed	
Quality Assurance	Adherence/ Competence	Fidelity rater			20% of s	essions (per schedule sent	by study sta	tistician)
	Inter-rater Reliability	IE		15% of sessions (per schedule sent by study statist					tistician)

*Data collected during the screening is part of routine clinical care; Wk=Week; Mo=Month; FU=Follow-up; Tx=Treatment; IE=Independent Evaluator; MD/RN=Physician/Nurse; ¹The CGI-I will not be administered at the screening or baseline, as it captures post-baseline improvement; ²Administered weekly if the CGI-I≥5 at any time; ³Information gathered by the RA will be reviewed by the therapist/instructor prior to each weekly class.

6.2 **Description of Evaluations** Assessment Instruments and Procedures

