7.1 Specification of Safety Parameters

A study MD or nurse with MD oversight will assess medical history and with consent will consult with PCPs if any medical issues that may potentially interfere with safe participation in yoga are identified. We have modified our study criteria to more clearly exclude all potential subjects with physical disabilities (evaluated with a medical history and physical exam) or cognitive disabilities (evaluated by the Montreal Cognitive Assessment Scale) that would clearly preclude safe practice of the yoga intervention or CBT. At present there is insufficient information regarding the safety of yoga during pregnancy. For reasons of safety, all women of childbearing potential will be required to use a reliable form of birth control throughout the study: (e.g.: oral contraceptives, surgical sterilization (of the subject or of her male partner), IUD (intrauterine device), condom and spermicide or diaphragm and spermicide). Subjects with existing or planned pregnancy during the intervention will be excluded. Inclusion of subjects

with any minor preexisting conditions of potential concern will be subject to participation only after consented review with and approval by the subject's primary healthcare provider.

Each visit, adverse events will be assessed on the adverse events monitoring form and rated as mild, moderate, or severe (as defined in AE section below). On weeks 0, 2, 4, 8, 10 and 12 the CGI-S, CGI-I, BDI and a suicidality checklist will be administered to evaluate any potential worsening symptoms. Physical fitness will be assessed by the study nurse with MD oversight or MD with the medical history form and a standard physical exam, emphasizing musculoskeletal, neurologic and cardiac history.

Twenty-four-hour emergency coverage with a study clinician (physician, psychologist or registered nurse with MD oversight) will be available. Patients will be provided with cards with the emergency contact number. In the event of an emergency the clinician will determine the necessary clinical intervention and will provide and coordinate appropriate care.

Parameters

All three interventions (Yoga, CBT, and SE) are safe interventions with minimal associated risk.

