9.5.2 Secondary Outcomes

Secondary Outcomes: Secondary outcome measures include the STAI, PSS, BDI-II and BAI, WHOQOL-BREF, PSQI, ISI, ASQ, and PSWQ. The FFMQ, MCQ, RSA, and cortisol are examined as possible mediators of change.

The Credibility/Expectancy Questionnaire will be administered to examine whether credibility and expectancy moderates therapy outcome.

In addition, we will explore whether clinical characteristics (comorbid diagnoses) and demographic characteristics (age, sex, SES) are possible moderators. The data analyses are described for the primary measure only.

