This growth curve model will be used to test differences between treatment conditions for our primary outcome (response to treatment) and for CGI-S, since these outcomes are measured frequently enough (7 times during treatment) to accurately model the growth curve. However, the other secondary outcomes are measured at most3 times during treatment (baseline, week 6, post-treatment), with secondary sleep measures administered only twice (baseline and posttreatment), thus disallowing accurate assessment of their growth curve. Thus, these outcomes will use an MRM employing an ANOVA type design (see for example, Liu, Rovine, & Molenaar, 2012). In this kind of model, time is treated as a categorical variable (using2 dummy variables [one for each assessment except the baseline assessment] to code the 3 assessments). The three treatment conditions (Yoga, CBT, and SE) will be coded using the 2 dummy variable contrasts (Yoga vs. SE and CBT vs. SE). Interactions will be formed between each treatment condition contrast and each assessment dummy variable. This coding freely estimates the means for the outcome at each assessment, without any constraint from a specific growth curve. This design is similar to a 3 x 3 repeated measures ANOVA with the exception that it includes all patients that complete at least one assessment, the outcome can be dichotomous, the covariance structure of the repeated measures can take almost any form, and this approach assumes data are missing at random (MAR) or not missing completely at random (MCAR). The significance of the interaction between a treatment condition contrast (e.g., Yoga vs. SE) and an assessment dummy variable (e.g., for the post-treatment assessment) will test whether the change from baseline to that assessment is significantly different between the treatment conditions. Using this coding scheme, all contrasts between treatment conditions at all assessments are provided by this one analysis. Thus, this approach has the added benefit of having all contrasts between the treatment conditions at each assessment being conducted on the same sample.

Demographics and comorbid diagnoses will be used as covariates in all analyses and considered as possible moderators of outcome at each assessment. An additional moderator that will be investigated is homework adherence.

Planned Secondary Analysis of Sensitivity of Growth Curve Model for Primary Outcome

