To determine if the results of the analyses for Aim 1 are sensitive to the growth curve model, we will perform a secondary analysis, using a simple ANCOVA-type model, to verify the results of our primary growth curve model. Since the outcome is binary (response to treatment), this analysis will be performed using logistic regression, with the following predictors of outcome at post-treatment: baseline severity based on the CGI-S and SIGH-A, and the two dummy variables coding the contrast between SE and the 2 active treatments. This analysis will be performed twice: once as an ITT analysis with missing outcomes imputed as last observation carried forward, and once as a completer analysis.

Per Protocol Secondary Analysis:

As additional secondary analyses, we will repeat our GLMM and MRM analyses using the per protocol sample. We will use these analyses rather than simpler analyses (such as logistic regression or repeated measures ANOVA) because repeating our GLMM and MRMs will allow a more direct comparison to the results for the intent-to-treat sample, allows inclusion of subjects that miss some assessments (other than baseline and post-treatment), allows the modeling of complex covariances between the repeated measures, and it assumes MAR rather than MCAR.

Follow Up Secondary Analyses:

Analyses of outcome at FU (Aim 2) will be considered exploratory since subjects may seek additional treatment during follow-up. These analyses will follow the analyses of outcome at post-treatment, except one additional assessment (FU) will be added to these analyses. Since response during FU may not follow the growth curve of the treatment phase, the growth curve for Aim 2 will be modeled as "piecewise", separately modeling the growth curve during treatment and follow-up. (Analyses of the secondary outcomes at FU will follow the mixed effects ANOVA model described above since these analyses include only 4 total assessments). We will add an additional dummy variable predictor to the analyses for Aim 2, coding whether or not the subject received additional treatment during FU. We will also add the interactions of this "additional treatment" variable with all the other predictors in the analyses to determine if "additional treatment" impacted response to treatment at FU. This analysis will

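### Section 9.6 counts at most three during-treatment assessments for secondary outcomes other than CGI-S, but the schedule gives the BAI, and section 7.1 the BDI, more, so the written model leaves collected ratings unused; the cost is modest.

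*Combined protocol and SAP*

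**What the plan says.** Section 9.6 divides the outcomes by how often they are measured. Response and CGI-S get a growth curve because they are "measured frequently enough (7 times during treatment) to accurately model the growth curve". For the rest it says that "the other secondary outcomes are measured at most3 times during treatment (baseline, week 6, post-treatment"), with the sleep measures taken only twice. These outcomes get a categorical-time mixed model with two time dummies "to code the 3 assessments". For follow-up, the same section keeps this model on the ground that "these analyses include only 4 total assessments".

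Section 9.5.2 lists the outcomes concerned: "Secondary outcome measures include the STAI, PSS, BDI-II and BAI, WHOQOL-BREF, PSQI, ISI, ASQ, and PSWQ".

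Two other places bear on the count:

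- The section 6.1 table marks the BAI biweekly between the main visits, with no arm restriction. The PSWQ row, by contrast, is restricted: "X (weekly if in CBT".
- Section 7.1, on safety, says: "On weeks 0, 2, 4, 8, 10 and 12 the CGI-S, CGI-I, BDI and a suicidality checklist will be administered". It names the BDI, not the BAI.

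**The concern.** The reason given for the three-assessment model does not fit every outcome sent to it. If the BAI is rated as often as CGI-S, the model as written uses three of its seven ratings. For a patient last seen at week 10 it knows nothing after week 6; for one last seen at week 4 it knows only baseline.

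The plan relies on data being missing at random, and that assumption is conditional on the data in the model. If patients leave because of a recent score that was recorded but left out, loss that would have been ignorable depends, for that model, on data it does not see. The arm means at week 12 can then be wrong, and so can their difference if the arms are affected unequally.

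There is also a prespecification gap. By the plan's criterion of frequency the BAI belongs with CGI-S; by its list it belongs with the sparse outcomes. An analyst could defend either model after seeing the data.

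**Working it through.** **1. The count.** The stated maximum is 3 (weeks 0, 6 and 12).

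- *BAI, section 6.1.* The table is damaged in the text available for this review. The BAI row carries six X marks, which fill the six columns from week 0 to follow-up, and two biweekly labels, which fit weeks 1-5 and 7-11. That gives weeks 0, 2, 4, 6, 8, 10 and 12: 7 during treatment and 8 with follow-up, against the stated 3 and 4. The ratings left unused are 7 - 3 = 4 (weeks 2, 4, 8 and 10).
- *BDI, section 7.1.* Six weeks are listed. Section 6.1 adds week 6, which again makes 7.

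The stated maximum is not reproduced on either reading.

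**2. Precision.** The documents give no within-patient correlation for the BAI, so a range was assumed: compound symmetry 0.5-0.7, AR(1) 0.8-0.9 per two weeks, and random intercept plus slope. For Yoga vs SE (95 vs 40, section 9.2 and Précis) with random loss of 20% (section 3) or 25% (section 9.2), using all seven ratings lowers the variance of the week-12 change contrast by 0.7% to 4.6%. When all loss falls after week 6:

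- weeks 8 and 10 alone give 0.8-4.6%;
- weeks 2 and 4 alone give 0% under AR(1) and 1.3-2.5% under the other structures.

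**3. Bias.** Assumed covariance at a lag of k two-week steps: 0.5 + 0.35 × 0.8^k, plus 0.15 on the diagonal. The week 0 to week 12 correlation is 0.5 + 0.35 × 0.8^6 = 0.59. The true difference in change is -0.40 SD. Dropout depends on the last observed score, with about 21-24% lost per arm and 400,000 simulated patients per arm. Simulation error is about √(2 × 2(1 - 0.59)/400,000) = 0.002.

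| Dependence of dropout on last score | 7 ratings | 3 ratings | Bias, 3 ratings |
|---|---|---|---|
| Same in both arms | -0.402 | -0.402 | none |
| One arm only | -0.398 to -0.402 | -0.363 to -0.372 | 0.028/0.40 = 7% to 0.037/0.40 = 9% |
| Opposite in the two arms | -0.399 to -0.401 | -0.442, -0.472 or -0.348 | 0.042/0.40 = 11% to 0.072/0.40 = 18% |

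The bias can go in either direction. The seven-rating model was unbiased throughout, up to simulation error.

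**4. Sensitivity to the covariance.** With about 25% lost, all after week 6, and the other structures above, the three-rating model misstates the affected arm's week-12 mean by 0.029 to 0.062 SD. Adding weeks 8 and 10 removes this; adding only weeks 2 and 4 does not. With all loss before week 6 the error is 0.030 to 0.060 SD, and there weeks 2 and 4 remove it. In one arm only, 0.062 SD would be 0.062/0.40 = 16% of the assumed difference.

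**5. Scale.** The complete-data standard error of the contrast is √(2(1 - 0.59) × (1/95 + 1/40)) = √(0.82 × 0.0355) = 0.17 SD. A bias of 0.028 to 0.072 SD is therefore about 0.2 to 0.4 standard errors.

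**The case against.** *It is not certain which outcome is biweekly.* The second biweekly mark in the BAI row sits out of column in the extracted text, and neighbouring rows are displaced. The BDI-II row has stray fragments under weeks 1-5 and 7-11, section 7.1 names the BDI, and section 8.1 gives the BDI-II a monitoring role through its suicidality item. This stands as a reason to check the original table. It does not rescue the count, because either reading leaves a secondary outcome with more than three ratings.

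*The bias needs a particular mechanism.* A reader might infer that the BAI contrast is simply biased. The documents do not support that. They say nothing about why patients would leave, and equal dependence in the arms gives no bias in the contrast. This objection stands in full.

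*All four unused ratings inform late dropouts.* A reader might infer this too. It is mainly weeks 8 and 10 that do so; weeks 2 and 4 serve mainly the early dropouts.

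*The plan has other safeguards.* Section 9.6 reruns the analyses by missing-data pattern, including late dropouts, and section 8.1 encourages a final assessment after treatment stops, so leaving treatment need not mean a missing week-12 score. Both reduce the harm. Neither puts the unused ratings into the model.

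*The rule corrects itself.* One dummy per post-baseline assessment extends naturally to seven visits. That is so once the count is right, but as written the plan fixes the number at two.

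**Conclusion.** The counting error is real: section 9.6 states a maximum of three (four with follow-up), while the schedule implies seven (eight) for the BAI, and section 7.1 points to the BDI. At least one secondary outcome is affected, and the written model discards collected data.

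The consequence is modest. It is about 1-5% of variance under random dropout, and no bias in the contrast when dropout depends on recent scores equally across arms. Under the main assumed covariance with about 21-24% loss, the bias is roughly 7-9% for dependence in one arm and 11-18% for opposite dependence. The one-arm figure could reach about 16% under a harsher structure with all loss late. All the bias figures rest on assumed correlations, an assumed dropout mechanism and an assumed difference of 0.40 SD, since the documents supply none of these for the BAI.

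A reader might infer that the trial's main conclusion is at risk. It is not: response, the primary outcome, already uses all seven assessments.

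**What to change.** - Reconcile section 6.1 with section 7.1 on whether the BAI, the BDI-II or both are rated biweekly.
- Correct the counts in section 9.6, both the three during treatment and the four with follow-up.
- For each outcome rated biweekly in all arms, fit the categorical-time model to all seven ratings with six time dummies and read the same week-12 contrast. Otherwise, state why only weeks 0, 6 and 12 are used.
- Keep the three-assessment model for outcomes with three assessments common to all arms.
- State that the weekly PSWQ ratings taken only in CBT are not used in the between-arm model.

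No new visits or data are needed. The model does grow: 2 × 6 = 12 treatment-by-time interactions instead of 2 × 2 = 4, and up to 7 × 8/2 = 28 covariance parameters instead of 3 × 4/2 = 6, with 40 patients in SE and a cohort level to fit as well. Name a structured covariance in advance as the fallback if the unstructured one does not converge.
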